### 3.2. Number of Subjects

Approximately 280 subjects will be enrolled, with targets based on GT and compensated cirrhosis status ([Table 1](#)). A blood sample for genotyping will be collected at screening. Genotype results at screening are generally not required to initiate dosing. However, as the study progresses, the Sponsor may use results to help manage these enrollment targets.

A lead-in group of 60 non-cirrhotic subjects will be enrolled and evaluated for SVR4; enrollment will open to the remaining 220 subjects provided that CCI [REDACTED] in the lead-in group experience virologic failure that was not due to poor compliance, and no study stopping rules are met (Section 5.6.3). Of the 60 subjects in the lead-in group, a target of 15 GT3-infected subjects will be enrolled; the remainder will be of any GT.

**Table 1: Planned Study Enrollment**

Total Number	Genotype	Enrollment Targets	Fibrosis Stage
N = 280	1a	n = 75	F0-F4 (Target: 20% with compensated cirrhosis)
	1b	n = 40	
	2	n = 40	
	3	n = 75	
	4	n = 25	
	5, 6, or 7	n = 25	F0-F4 (No specified target for compensated cirrhosis)

## 4. SUBJECT SELECTION

### 4.1. Study Population

Subjects must meet all the inclusion criteria and none of the exclusion criteria to be eligible for participation in this study. A signed copy of the informed consent form will be provided to each subject.

Both eligible males and females between 18 and 85 (inclusive) years of age will be enrolled in the study. HCV disproportionately affects more men than women, and prevalence is higher in people over 50 years. However, in people who inject drugs or engage in behaviors that increase the risk of transmitting bloodborne diseases, the risk for acquiring HCV is elevated regardless of sex or age. As such, including both males and females across the adult lifespan ensures that enrolled subjects represent the diversity of the patient population. In addition, current nonclinical data supports enrolling females of childbearing potential and male subjects with childbearing-potential partners provided acceptable effective contraception is used, as specified in Section 5.9.

### 4.2. Inclusion Criteria

1. Willing and able to provide written informed consent
2. Male or female subjects between  $\geq 18$  years of age (or the legal age of consent per local regulations) and  $\leq 85$  years of age
3. Fridericia-corrected QT (QTcF) interval  $\leq 440$  ms for males and  $\leq 460$  ms for females at Screening  
*Note: The mean of the triplicate readings, rounded to the nearest whole number, should be used to assess the QTcF.*
4. Female subjects of childbearing potential: agreement to remain abstinent (refrain from heterosexual intercourse) or to the use of an acceptable effective contraception, as described in Section 5.9
5. Females of childbearing potential must have a negative pregnancy test at Screening and at Day 1 prior to dosing
6. Subjects must be DAA-treatment-naïve, defined as never exposed to an approved or experimental DAA for HCV  
*Note: Prior exposure to (peg)interferon with or without ribavirin is acceptable, as long as it/they were not administered with a DAA.*
7. Willingness to provide a blood sample at Screening for genotyping.
8. Documented medical history compatible with chronic HCV, including any one of the following:
  - a. positive for anti-HCV antibody, HCV RNA, or an HCV GT at least 6 months prior to Day 1, or
  - b. positive for anti-HCV antibody at Screening with clinical or laboratory evidence of chronic HCV disease, such as the presence of fibrosis by biopsy or noninvasive tests

9. HCV RNA  $\geq$  1,000 IU/mL at Screening.
10. Liver disease staging assessment as follows:
  - Absence of cirrhosis (F0 to F3) defined as any one of the following:
    - Liver biopsy within 24 months of Day 1 showing absence of cirrhosis
    - Fibroscan® within 12 months of Day 1 with a result of  $\leq$  12.5 kPa
    - Fibrosure® (Fibrotest®) performed during screening with a score of  $\leq$  0.48 and an aspartate aminotransferase (AST)-to-platelet ratio index (APRI) of  $\leq$  1
  - Compensated cirrhosis (F4) defined as any one of the following:
    - Liver biopsy performed prior to Day 1 showing cirrhosis (Metavir stage 4 or equivalent)
    - Fibroscan® within 12 months of Day 1 showing cirrhosis with result  $>$  12.5 kPa
    - Fibrosure® (Fibrotest®) performed during screening with a score of  $>$  0.75 and an APRI of  $>$  2

*NOTE: Subjects in the lead-in group must not have F4 cirrhosis*

*APRI formula: AST  $\div$  lab upper limit of normal (ULN) for AST  $\times$  100  $\div$  (platelet count  $\div$  100).*

*NOTE: In the absence of a definitive diagnosis of presence or absence of cirrhosis by the above criteria, a liver biopsy or Fibroscan® is required. Liver biopsy results supersede the results obtained by Fibroscan® or Fibrosure®.*

11. Subject is, in the opinion of the investigator, willing and able to comply with the study drug regimen and all other study requirements

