**Diagnosis and Main Criteria for Inclusion:**

**Inclusion Criteria:**

1. Willing and able to provide written informed consent
2. Male or female subjects between  $\geq$  18 years of age (or the legal age of consent per local regulations) and  $\leq$  85 years of age
3. Fridericia-corrected QT (QTcF) interval  $\leq$  440 ms for males and  $\leq$  460 ms for females at Screening

*Note: The mean of the triplicate readings, rounded to the nearest whole number, should be used to assess the QTcF.*

4. Female subjects of childbearing potential: agreement to remain abstinent (refrain from heterosexual intercourse) or to the use of an acceptable effective contraception, as described in Section 5.9
5. Females of childbearing potential must have a negative pregnancy test at Screening and at Day 1 prior to dosing
6. Subjects must be direct-acting antiviral (DAA)-treatment-naïve, defined as never exposed to an approved or experimental DAA for HCV  
*Note: Prior exposure to (peg)interferon with or without ribavirin is acceptable, as long as it/they were not administered with a DAA.*
7. Willingness to provide a blood sample at Screening for genotyping.
8. Documented medical history compatible with chronic HCV, including any one of the following:
  - positive for anti-HCV antibody, HCV RNA, or an HCV GT at least 6 months prior to Day 1, or
  - positive for anti-HCV antibody at Screening with clinical or laboratory evidence of chronic HCV disease, such as the presence of fibrosis by biopsy or noninvasive tests
9. HCV RNA  $\geq$  1,000 IU/mL at Screening.
10. Liver disease staging assessment as follows:
  - Absence of cirrhosis (F0 to F3) defined as any one of the following:
    - Liver biopsy within 24 months of Day 1 showing absence of cirrhosis
    - Fibroscan® within 12 months of Day 1 with a result of  $\leq$  12.5 kPa
    - Fibrosure® (Fibrotest®) performed during screening with a score of  $\leq$  0.48 and an aspartate aminotransferase (AST)-to-platelet ratio index (APRI) of  $\leq$  1
  - Compensated cirrhosis (F4) defined as any one of the following:
    - Liver biopsy performed prior to Day 1 showing cirrhosis (Metavir stage 4 or equivalent)
    - Fibroscan® within 12 months of Day 1 showing cirrhosis with result  $>$  12.5 kPa
    - Fibrosure® (Fibrotest®) performed during screening with a score of  $>$  0.75 and an APRI of  $>$  2

*APRI formula:  $AST \div \text{lab upper limit of normal (ULN) for AST} \times 100 \div (\text{platelet count} \div 100)$ .*

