- Alanine aminotransferase (ALT) or AST > 10 x ULN
- Total bilirubin > 3 mg/dL (> 51.3  $\mu$ mol/L)
- Albumin < 2.8 g/dL (< 28 g/L)
- International Normalized Ratio (INR) > 2.2 unless subject has a stable INR on an anticoagulant
- Hemoglobin < 10 g/dL
- Hemoglobin A1c (HbA1c) > 8.5%
- Platelet count < 50 x 10^9/L

- Estimated glomerular filtration rate (eGFR) < 30 mL/min/1.73 m^2 as estimated by the Modification of Diet in Renal Disease (MDRD) formula
- Concomitant grade  $\geq 2$  toxicity of both lipase and amylase per Division of AIDS criteria (<https://rsc.niaid.nih.gov/sites/default/files/daidsggradingcorrectedv21.pdf>)

*Note: Retests of Screening laboratory parameters or assessments may be permitted once in certain scenarios with medical monitor approval. Such scenarios may include lab processing error, results inconsistent with subject's historical values/medical history, or other extenuating circumstances such as a recent or intercurrent illness potentially affecting Screening laboratory results.*

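### The APRI formula in inclusion criterion 10 divides platelets by 100 and gives no platelet unit, so its cut-offs of 1 and 2 cannot both work and cirrhosis status can be assigned without real APRI support

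*Protocol*

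**What the plan says.** Criterion 10 (Protocol Section 4.2, repeated in the synopsis) offers three alternative staging routes: biopsy, Fibroscan, or Fibrosure combined with APRI.

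- **No cirrhosis by the third route:** Fibrosure ≤ 0.48 and "aspartate aminotransferase (AST)-to-platelet ratio index (APRI) of $\leq$ 1".
- **F4 by the third route:** Fibrosure "performed during screening with a score of $>$ 0.75 and an APRI of $>$ 2".
- **Formula:** AST ÷ "lab upper limit of normal (ULN) for AST $\times$ 100 $\div$ (platelet count $\div$ 100"). The synopsis prints the same division: "100 \div (\text{platelet count} \div 100"). Neither place gives a platelet unit.
- **Fallback:** if these rules do not settle the matter, biopsy or Fibroscan must be done, and biopsy overrides the other two.
- **Lead-in:** "NOTE: Subjects in the lead-in group must not have F4 cirrhosis".

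Section 4.3, criterion 13, bounds the inputs by excluding "Alanine aminotransferase (ALT) or AST > 10 x ULN" and "Platelet count < 50 x 10 9 /L". SAP Section 4.5 lists APRI as a screening assessment but gives no formula.

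**The concern.** The formula multiplies by 100 and then also divides the platelet count by 100, so the two factors compound. An index built that way should be checked against cut-offs as small as 1 and 2.

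If the cut-offs do not separate eligible subjects, the APRI half of the third route stops contributing, and the label rests on Fibrosure alone or is never given. Cirrhosis status has three uses in the plan: it bars F4 subjects from the 60-subject lead-in, it defines the 20% cirrhosis enrolment target (Table 1), and it splits every efficacy result (Protocol Section 8; SAP Section 8.5).

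**Working it through.** The documents contain no worked APRI value, so there is no figure to reproduce. The check evaluates the printed formula over the protocol's own eligible range.

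**Inputs from the documents.** AST ≤ 10 × ULN; platelets ≥ 50 × 10^9/L, which is 50,000/µL; cut-offs ≤ 1 and > 2.

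**Assumed inputs.** The documents set no lower limit for AST and no upper limit for platelets. Illustrative values are AST from 0.5 × ULN and platelets up to 400 or 450 × 10^9/L.

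**Step 1: simplify.** (AST/ULN) × 100 ÷ (platelets ÷ 100) = 10,000 × (AST/ULN) ÷ platelets.

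**Step 2: platelets in 10^9/L, the unit used in Section 4.3.**
- AST = 1 × ULN, platelets 250: 10,000 ÷ 250 = 40.
- APRI ≤ 1 needs AST/ULN ≤ platelets ÷ 10,000. At platelets 200 that is 0.02; even at 450 it is 0.045. No plausible subject meets it.
- APRI > 2 needs AST/ULN > platelets ÷ 5,000. At 450 that is 0.09, so it is effectively automatic.
- Example: Fibrosure > 0.75, AST 1 × ULN, platelets 200. Printed APRI is 50, so the label is F4. Without the extra division, APRI is 100 ÷ 200 = 0.5, which does not support F4.

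**Step 3: platelets in cells/µL.**
- The largest value an eligible subject can reach is 10,000 × 10 ÷ 50,000 = 2.0. A value above 2 is impossible, and this follows from the protocol's limits alone.
- APRI ≤ 1 fails only if AST/ULN exceeds platelets ÷ 10,000. Within the eligible limits that requires AST above 5 × ULN and platelets below 100,000/µL. Elsewhere it is automatic.
- Example: Fibrosure ≤ 0.48, AST 3 × ULN, platelets 60,000/µL. Printed APRI is 30,000 ÷ 60,000 = 0.5, so the label is non-cirrhotic. Without the extra division, APRI is 300 ÷ 60 = 5, and the subject would be unresolved and sent to biopsy or Fibroscan.

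**Step 4: without the extra division, platelets in 10^9/L.** APRI = 100 × (AST/ULN) ÷ platelets.
- Range under the assumptions: 0.5 × 100 ÷ 400 = 0.125 up to 10 × 100 ÷ 50 = 20.
- At platelets 200, APRI reaches 1 at AST 2 × ULN and 2 at 4 × ULN. Both cut-offs now separate subjects.
- Against this version, the printed formula is 100 times higher in 10^9/L and 10 times lower in cells/µL.

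| Platelet unit | APRI ≤ 1 (with Fibrosure ≤ 0.48) | APRI > 2 (with Fibrosure > 0.75) |
|---|---|---|
| 10^9/L, as printed | never met | always met |
| cells/µL, as printed | nearly always met | never met |
| 10^9/L, no extra division | separates subjects | separates subjects |

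**The case against.** The strongest reply is that the formula is wrong but does little harm, and much of that stands.

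- **The fallback absorbs an unreachable branch.** A subject who cannot satisfy either definition is referred for biopsy or Fibroscan, which means an extra test and not a wrong label. Subjects staged by biopsy or Fibroscan are unaffected.
- **Fibrosure gates both branches.** Because ≤ 0.48 and > 0.75 do not overlap, the formula cannot move anyone from one definition to the other. Where it yields an unsupported label, a working rule would have returned an unresolved result, not the opposite status.
- **Actual use is unknown.** Protocol Section 6.6 sends samples to a central laboratory and also allows local results at Screening. No section says who computes APRI, or whether the printed line was applied literally.

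A reader might infer that cirrhosis status is misassigned throughout the trial. The documents do not support that: the exposure is confined to discordant subjects on one of three routes.

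A reader might also infer that the lead-in, the enrolment target and the subgroup results are all compromised together. No single unit does this. In 10^9/L the route cannot label anyone non-cirrhotic, so it cannot admit an F4 subject to the lead-in. In cells/µL it cannot label anyone F4, so it cannot add false F4 subjects to the target.

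What the reply does not rescue is the rule itself. The formula appears the same way twice, which makes a text-extraction fault unlikely, and it fails in either usual unit.

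**Conclusion.** The point holds as a defect in a written eligibility and staging rule, with limited and conditional consequences. As printed, the two APRI cut-offs cannot both function within the protocol's own limits. In cells/µL this is proved by those limits; in 10^9/L it also needs the mild assumption that AST is not below about 0.045 × ULN at platelets up to 450.

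The result is that F4 status (10^9/L) or non-cirrhotic status (cells/µL) can be assigned without the APRI support the protocol intends. This applies to subjects staged by Fibrosure + APRI whose two results disagree. Neither their number nor the share of subjects staged by this route can be derived from the documents.

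The exposed uses depend on the unit: the cirrhosis target in 10^9/L, lead-in eligibility in cells/µL, and the breakdown by cirrhotic status in both.

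It would be tempting to say that the primary result is affected. Protocol Section 8.4.1 pools SVR12 over cirrhosis status, and both non-cirrhotic and compensated cirrhotic subjects are eligible for the study, so the label does not enter that estimate directly. The per-protocol populations do require all eligibility criteria to be met. The formula would reach them only if compliance with criterion 10 were judged against the printed line, which the documents do not say.

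**What to change.** Reconcile the formula, the platelet unit and the two cut-offs in Protocol Section 4.2 and in the synopsis, and state the unit beside the formula. One repair leaves both cut-offs unchanged: drop the division of platelets by 100 and specify 10^9/L. Dividing a cells/µL count by 1,000 gives the same number. Either puts both cut-offs inside the eligible range, about 0.1 to 20 under the stated assumptions.

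State who computes APRI. Before the analyses by cirrhotic status, recompute it for every subject staged by Fibrosure + APRI, and list those whose label was not supported by a working APRI.

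The cost is one line in two places and a data check on AST and platelet values already collected. No new visits, samples or sample-size work are needed for the recomputation.

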#### **4.3. Exclusion Criteria**

1. Female subject is pregnant or breastfeeding
2. Co-infected with hepatitis B virus (HBV, positive for hepatitis B surface antigen [HBsAg]) and/or human immunodeficiency virus (HIV)
3. Abuse of alcohol and/or illicit drug use that could interfere with adherence to study requirements as judged by the investigator
4. Prior exposure to any HCV DAA
5. Requirement of any prohibited medications, as described in Section 5.8
6. Use of other investigational drugs within 30 days of dosing or plans to enroll in another clinical trial of an investigational agent while participating in the present study
7. Subject with known allergy to the study medication(s) or any of their components

8. History or signs of decompensated liver disease: ascites, variceal bleeding, hepatic encephalopathy, spontaneous bacterial peritonitis, or other clinical signs of portal hypertension or hepatic insufficiency

9. Cirrhotic and has a Child-Pugh score >6, corresponding to a Child-Pugh Class B or C.

*Note: To calculate the Child-Pugh score, refer to the following website:*

<https://www.mdcalc.com/calc/340/child-pugh-score-cirrhosis-mortality>

10. History of hepatocellular carcinoma (HCC) or findings suggestive of possible HCC

11. Active clinically significant diseases including:

- Evidence of history of chronic hepatitis not caused by HCV, including drug-induced hepatitis, hemochromatosis, Wilson's disease, alpha-1-antitrypsin deficiency, alcoholic liver disease, and autoimmune hepatitis
- Cardiac abnormalities/dysfunction that may interfere with subject treatment, assessment, or compliance with the protocol, including unstable angina, unstable congestive heart failure and unstable arrhythmia
- Malignant disease or suspicion or history of malignant disease within previous 5 years (except for adequately treated basal or basosquamous cell carcinoma)
- Any medical condition requiring chronic use of immunosuppressive drugs (e.g., for organ transplantation).
- Subject with intestinal malabsorption (eg, structural defects, digestive failure, or enzyme deficiencies with the exception of lactose intolerance)
- Any other clinically significant medical condition that, in the opinion of the investigator, would jeopardize the safety of the subject or impact the validity of the study results

12. Clinically significant abnormal ECG at Screening, as determined by the investigator.

13. Any of the following laboratory parameters at Screening:

- Alanine aminotransferase (ALT) or AST > 10 x ULN
- Total bilirubin > 3 mg/dL (> 51.3  $\mu$ mol/L)
- Albumin < 2.8 g/dL (< 28 g/L)
- International Normalized Ratio (INR) > 2.2 unless subject has a stable INR on an anticoagulant
- Hemoglobin < 10 g/dL
- Hemoglobin A1c (HbA1c) > 8.5%
- Platelet count < 50 x 10^9/L

- Estimated glomerular filtration rate (eGFR) < 30 mL/min/1.73 m^2 as estimated by the Modification of Diet in Renal Disease (MDRD) formula
- Concomitant grade  $\geq 2$  toxicity of both lipase and amylase per Division of AIDS criteria (<https://rsc.niaid.nih.gov/sites/default/files/daidsggradingcorrectedv21.pdf>)

*Note: Retests of Screening laboratory parameters or assessments may be permitted once in certain scenarios with medical monitor approval. Such scenarios may include lab processing error, results inconsistent with subject's historical values/medical history, or other extenuating circumstances such as a recent or intercurrent illness potentially affecting Screening laboratory results.*

## 5. STUDY TREATMENTS

### 5.1. Description and Handling of Study Treatments

#### 5.1.1. Test Products

The study drugs will be provided by the Sponsor. BEM (manufactured by CCI [REDACTED] or CCI [REDACTED]) will be provided as 275-mg tablets (A2--275 mg tablets). RZR (manufactured by CCI [REDACTED]) will be provided as 90-mg capsules.

Neither of the study drugs are authorized for marketing in any country. Justification for the doses is provided in Section 1.2.

#### 5.1.2. Control Product(s)

No control products will be used in this study.

#### 5.1.3. Packaging and Labeling

The Sponsor will be responsible for ensuring that study drug(s) are manufactured in accordance with applicable Good Manufacturing Practice regulations and requirements. The labels for the study drug(s) will meet applicable local regulatory requirements. Refer to the Pharmacy Manual for specific labeling information.

#### 5.1.4. Storage and Handling

Study drugs should be stored and handled under the conditions described on the label.

## 5.2. Method of Assigning Subjects to Treatment

A unique subject number will be assigned to each subject at Screening. Once assigned, it will not be re-assigned to another subject. All subjects will receive the same treatment regimen of BEM and RZR for 8 weeks.

## 5.3. Blinding

This study is not blinded.

## 5.4. Dosing and Administration

### 5.4.1. Dispensing

Site staff will administer the first dose of study drugs at each subject's Day 1 visit. Site staff will supply each subject with enough study drug.

### 5.4.2. Administration Instructions

Subjects will take two (2) 275-mg tablets of BEM and two (2) 90-mg capsules of RZR once daily for 8 weeks (56 days). Study drugs will be taken together orally in the morning, at

approximately the same time each day. Study drugs can be taken with water and with or without food.

For missed dose(s), subjects will be instructed to take the missed dose(s) of study drugs as soon as possible during the same day. Subjects will be instructed not to double the next dose with a missed dose (doses should be a minimum of 6 hours apart).

In case of an incomplete dose (i.e., 1 or more tablets and/or capsules missed), the subject should take the rest of the missed tablets and/or capsules as soon as possible on the same day; they should not add the rest of the missed dose to their next dose and take more than 2 BEM tablets and 2 RZR capsules at the next dose.

Subjects will receive their first dose of study drugs in the clinic on Day 1. Thereafter subjects may self-administer the study drugs at home except for subjects who agree to additional PK and/or PK-VK sampling as part of a substudy. These subjects will be required to take their study drug in the clinic on certain days (see Section 5.4.3 and Table 3).

#### **5.4.3. Dosing for Optional PK-only Substudy and PK-VK Substudy**

Subjects participating in the optional serial PK-only substudy and/or the optional PK-VK substudy will have additional blood samples collected at certain visits. The first samples will be collected pre-dose so study staff will remind these subjects not to take study drugs on the substudy visit days until instructed to do so during the visit (see Section 6.7). The date and time of the sample collections and dosing will be recorded.

#### **5.4.4. Treatment Compliance**

Subjects will be instructed to bring back all bottles of study drugs in their original containers at every study visit through EOT. Study drug dosing by the subjects will be reconciled using pill counts at each visit by the investigator or designee to monitor adherence to the dosing regimen. In addition, subjects may be contacted by site staff or visited by home nursing between scheduled visits to ensure compliance with the dosing schedule.

### **5.5. Study Drug Accountability**

Investigators or designees will facilitate study drug accountability by maintaining complete and accurate records of all study drugs. These include acknowledging the receipt of each shipment of study drug, maintaining subject dispensing records, and accounting for returned or destroyed study drug.

At EOS (see Section 3.1), all unused study drugs and containers will be returned to the Sponsor (or designee) or destroyed, per the instruction of the Sponsor.

